3.0 OBJECTIVES AND ENDPOINTS

Table 1 Study Objectives and Endpoints

Objectives	Endpoints
Efficacy	Primary Efficacy

 To investigate the efficacy of two concentrations of topically applied TMB-001 as a treatment for congenital ichthyosis (CI) of either the autosomal recessive congenital ichthyosis-lamellar ichthyosis (ARCI-LI) or RXLI subtypes. 	Proportion of subjects with VIIS "treatment success" (VIIS-50), which is defined as a 50% or greater decrease in VIIS scaling score relative to Baseline at Visit 6 (EOS) calculated using the sum of the scores for 'VIIS body areas' that have a Baseline score ≥ 3 .
	Key Secondary Efficacy
	
 IGA scores, dichotomized to "treatment success" or "treatment failure" where "treatment success" is defined as at least a 2-grade decrease in severity score relative to Baseline at Visit 6 (EOS).
	Other Secondary Efficacy

 Time to achieve VIIS-50 ($\geq 50\%$ reduction in VIIS scaling score for body sites that had a Baseline score ≥ 3) that is maintained at the next observation. Changes in VIIS scaling score relative to Baseline at Visit 4 and Visit 5. Proportion of subjects with IGA "treatment success" at Visit 4, Visit 5, and Visit 6 (EOS). Proportion of subjects with an IGA score of 0 or 1 representing "cleared" or "almost cleared" at Visit 6 (EOS). Changes in percent BSA relative to Baseline with CI in the Treatment/Assessment Areas at Visit 3, Visit 4, Visit 5, and Visit 6 (EOS). Change from Baseline in I-NRS score at Visit 6 (EOS). Proportion of subjects with I-NRS "treatment success" where "success" is defined as at least a 4-point reduction in I-NRS relative to Baseline at Visit 6 (EOS). Change in DLQI from Baseline to Visit 6 (EOS). 	

Objectives	Endpoints
Safety	Safety

 • To investigate the safety of topically applied TMB-001. 	
 • Incidence (severity and causality) of any local and systemic AEs. • Number of subjects with presence (and severity) at each time point of the following LSRs: burning/stinging, erythema, erosions, and edema. • Changes from Baseline in vital signs at Visit 6 (EOS). • Changes from Baseline in clinical laboratory test results (chemistry, hematology, and urinalysis) at Visit 6 (EOS).

Abbreviations: AE = adverse event; ARCI-LI = autosomal recessive congenital ichthyosis-lamellar ichthyosis; BSA = body surface area; CI = congenital ichthyosis; DLQI = Dermatology Life Quality Index; EOS = End of Study; IGA = Investigator's Global Assessment; I-NRS = Itch-Numeric Rating Scale; LSR = local skin reaction; RXLI = recessive X-linked ichthyosis; VIIS = Visual Index for Ichthyosis Severity.

4.0 STUDY DESIGN

4.1 Overall Design

This is a randomized, parallel, double-blind, vehicle-controlled study to evaluate the safety and efficacy of two concentrations of topical TMB-001 for the treatment of CI in subjects with either the ARCI-LI or RXLI subtypes.

Approximately 10 study centers from United States of America and Australia are expected to participate in this global study.

The duration of treatment will be 12 weeks.

Each subject will participate in the study for up to 24 weeks (including up to a 90-day Screening period).

4.1.1 Treatment Groups

Eligible subjects will be randomized (1:1:1) to 1 of 3 treatment groups:

1. TMB-001 Ointment, 0.05%, bid
2. TMB-001 Ointment, 0.1%, bid
3. Vehicle Ointment (Control), 0%, bid

4.1.2 Treatment/Assessment Areas

Treatment/Assessment Areas are defined as:

4.1.2.1 Treatment Area

The area of the entire body with active CI where the study medication will be applied (the entire body except for the hands, face, neck, scalp and genitalia are possible treatment areas.)

4.1.2.2 *The Visual Index for Ichthyosis Severity (VIIS) Assessment Areas*

The primary efficacy assessment will be performed using the Visual Index for Ichthyosis Severity (VIIS). Four VIIS Assessment Areas will be defined as described below and will be further described using color illustrations in the Investigator Study Binder:

- (a) the upper back from the posterior axillary fold to the other encompassing the T1-T10,
- (b) the upper arm (excluding elbow), left or right,
- (c) the shin/lower leg (the portion below the proximal aspect of the knee cap), left or right
- (d) dorsal foot (left or right).

The Investigator will include subjects when any of the 4 VIIS Assessment Areas have some CI disease. At least 2 of the 4 VIIS Assessment Areas MUST have a scaling score of 3 or more. Since for (b), (c), and (d) each include two body parts, one of each left or right must be designated as the Target (upper arm, lower leg, or dorsal foot) and followed throughout the study for VIIS assessment. The arm, leg, or foot with more severe and higher score will be designated as the Target unless they have the same severity scores, in which case the left or right choice will be at the discretion of Investigator assuming no other issues exists, dictating the choice of left/right. The severity scores will be averaged by the electronic data capture system but the score of two body parts that have a score of 3 or higher will be used to enroll subjects and used in subsequent assessments. A five-point (0-4) scale will be used with increasing clinical severity (scaling) and will be defined in the training manual.

The primary efficacy endpoint will be the proportion of subjects with VIIS "treatment success" (VIIS-50), which is defined as a 50% or greater decrease in VIIS scaling score relative to Baseline at Visit 6, End of Study (EOS) calculated using **only** the VIIS body areas described above that have a Baseline score ≥ 3 .

VIIS severity will be calculated as above via one of two methods below

- On-site visual inspection of the VIIS areas
- Virtual/Remote visit comprised of both photographs and tele-medicine utilizing synchronous video-conferencing technology. The severity score at each visit will be based off information gathered from both sources to yield one score.

4.1.2.3 The Investigator's Global Assessment (IGA) Assessment Area

The IGA will be performed on the entire Treatment Area. The IGA assessment will inherently include the VIIS Area but it will provide a broader perspective on disease status and therapeutic response at baseline and subsequent visits. The IGA score is a static evaluation of the overall or "average" degree of severity of a subject's disease, considering all the subject's scaling and fissuring in the - Treatment Areas by the Investigator or designee. This evaluation takes into consideration the 2 individual characteristics of CI (scaling and fissuring) with the IGA score at each visit representing the average degree of scaling and fissuring that is eligible for treatment. The IGA will be assessed using the 5-point scale as shown in Table 3.

IGA severity will be calculated as above via one of two methods below:

- On-site visual inspection
- Virtual/Remote visit comprised of both photographs and tele-medicine utilizing synchronous video conferencing technology. The severity score at each visit will be based off information gathered from both sources to yield one score.

4.2 Scientific Rationale for Study Design

The proposed study will use a multicenter, randomized, double-blind, parallel group, vehicle-controlled study design to evaluate the efficacy and safety of 0.1% and 0.05% TMB-001 in the treatment of CI. The subjects will be selected according to predefined entry criteria. The study treatment duration is 12 weeks and expected to be enough to show a treatment effect.

Isotretinoin was first approved in the US by the FDA and formulated as an oral product, Accutane (isotretinoin) capsules, to treat severe recalcitrant nodular acne (9). A topical formulation of isotretinoin, Isotrex® (isotretinoin) gel, 0.05%, has been approved in various countries outside of the US for the treatment of mild to moderate inflammatory acne vulgaris (6). The pharmacology, pharmacokinetics, and toxicology of isotretinoin have been well characterized in the literature.

Isotretinoin is an approved active pharmacological ingredient with a long history of safe use in humans under the iPLEDGE program (18). The iPLEDGE program is a risk management distribution program mandated by the FDA for isotretinoin because isotretinoin must not be used by female patients who are or may become pregnant. There is an extremely high risk that severe birth defects will result if pregnancy occurs while taking oral isotretinoin in any amount, even for a short period of time. Potentially any fetus exposed during pregnancy can be affected.

4.3 Justification for Dose

The concentrations of TMB-001 ointment chosen for this study are based on the formulation integrity and Phase 2a clinical study, specific laboratory animal toxicology studies performed by the Sponsor, and a review of the published safety data for isotretinoin. The highest dose (0.2% topically applied ointment) tested in the Phase 2a clinical study was reported with retinoid dermatitis and lower tolerability, hence doses lower than 0.2% have been considered for this study. The doses to be applied, 0.1% and 0.05%, are based upon the potential for therapeutic benefit balanced with the safety risk.

4.4 End of Study Definition

A subject is considered to have completed the study if he/she has completed the last scheduled visit (Visit 6) per the Schedule of Activities (Section 1.2).

The end of the study is defined as the date of the last visit of the last subject in the study globally.

5.0 STUDY POPULATION

The subjects will be male and/or female subjects, 9 years of age and older, with moderate to severe CI genetically confirmed to be of either the ARCI-LI or RXLI subtypes according to protocol-specified definitions.

Prospective approval of protocol deviations to recruitment and enrollment criteria, also known as protocol waivers or exemptions, is not permitted.

5.1 Inclusion Criteria

To enter the study, a subject must meet the following criteria:

1. Subject is male or female, 9 years of age and older at Visit 2 (Baseline).
2. Subject has provided written informed consent/assent. A subject under 18 years of age must provide written informed assent and be accompanied by the parent or legal guardian at the time of consent/assent signing. The parent or legal guardian must provide informed consent for the subject. If a subject becomes 18 years of age during the study, the subject must provide written informed consent at that time to continue study participation.
3. Females must be postmenopausal (defined as amenorrhea greater than 12 consecutive months in women 50 years of age and older), surgically sterile (hysterectomy, bilateral salpingectomy, or bilateral oophorectomy), or use acceptable forms of birth control. Women of childbearing potential (WOCBP) must have a negative urine pregnancy test (UPT) at Visit 2 (Baseline) (UPTs must have a minimum sensitivity to detect 25 mIU beta-human chorionic gonadotropin [β -hCG]/mL). Methods of acceptable contraception are further defined in [Appendix 6](#). Female subjects who become sexually active or begin to have relations with a partner during the study must agree to use 2 forms of birth control for 30 days prior to having relations and to continue such forms for the duration of the study.
4. Subject has clinical diagnosis of CI and has a genetic confirmation of either ARCI-LI (eg, transglutaminase 1-deficient) or RXLI (eg, deletion of steroid sulfatase gene) subtypes of CI. For ARCI-LI subjects, enrollment is not limited to Transglutaminase 1 mutations. Other genetically confirmed ARCI-LI mutations can potentially be enrolled as long as the phenotype is consistent with ARCI-LI and the other inclusion criteria are met, as determined by the Investigator. Congenital Ichthyosis XomeDxSlice will be used to diagnose both RXLI and ARCI-LI. GeneDx tests detect transglutaminase mutations in the TGM1 gene, X-linked recessive steroid sulfatase mutations in the STS gene, and additionally analyzes 47 other genes linked to CI. This is a multi-gene panel testing so that all known causes of CI can be confirmed/ruled-out since there is phenotypic overlap between the subtypes (including STS). The tests are considered Laboratory Developed Tests (LDTs) and are thus regulated per US regulations 42 CFR 493 and the laboratory is accredited by the College of American Pathologists.

5. The amount of CI affected skin in the Treatment Area at Baseline will be between a minimum of 10% and maximum of 90% of the total BSA (1% BSA is approximately equal to the surface area of the subject's palm and fingers, with the fingers extended yet grouped together, creating a flat oval-like surface area).
6. Subject's designated VIIS assessment areas MUST:
 - Include any of the 4 VIIS assessment areas that have some CI disease involving: (a) the upper back from the posterior axillary fold to the other encompassing the T1-T10, (b) the upper arm (excluding elbows), left or right, (c) the shin/lower leg (the portion below the proximal aspect of the knee cap), left or right, and (d) dorsal foot (left or right); AND
 - At least 2 of the 4 VIIS assessment areas MUST have a scaling score of 3 or more.
7. Subject and parent/guardian (if applicable) are willing and able to apply the study treatment(s) as directed, comply with study instructions, and commit to all follow-up visits for the duration of the study.
8. Subject, in the Investigator's opinion, is in good general health and free of any disease state or physical condition that might impair evaluation of the Treatment/Assessment Areas or exposes the subject to an unacceptable risk by study participation.

5.2 Exclusion Criteria

A subject is ineligible to enter the study if he/she meets 1 or more of the following criteria:

1. Subject is pregnant, lactating, or is planning to become pregnant during the study.
2. Subject has inflammatory skin diseases that confound the interpretation of results (eg, atopic dermatitis) unrelated to ichthyosis.
3. Subject has previously failed on topical/oral retinoid therapy for treatment of CI.
4. Subject, in the Treatment/Assessment Areas, has used: (a) topical retinoids or any other topical prescription or over-the-counter therapies (except emollients, keratolytics, and topical steroids - see below), that are intended for, or that in the opinion of the Investigator, may improve CI within 2 weeks of Visit 2 (Baseline), or (b) keratolytics or topical corticosteroids within 5 days prior to Visit 2 (Baseline).
5. Subject has used any topical products in the Treatment/Assessment Areas, including bland emollients, on Visit 2 (Baseline) prior to randomization.
6. Subject has used ultraviolet (UV) treatment within 4 weeks prior to Visit 2 (Baseline).
7. Subject has undergone systemic therapies using vitamin A supplements or St. John's Wort within 4 weeks prior to Visit 2 (Baseline). Note: Use of a multivitamin including Vitamin A is not exclusionary provided it is taken as directed on the packaging.
8. Subject has used systemic retinoids within 12 weeks of Visit 2 (Baseline) or any other systemic therapies that are intended for or may improve CI within 4 weeks of Visit 2 (Baseline).
9. Subject is immunosuppressed (eg, human immunodeficiency virus, systemic malignancy, graft host disease) or receives systemic immunotherapy.

10. Subject is currently taking concomitant immunosuppressive drugs, including systemic corticosteroids, within 2 weeks of Visit 2 (Baseline).
11. Subject has untreated secondary infections; however, subject may become eligible after successful treatment of his/her infection(s) at the Investigator's discretion.
12. Subject is currently enrolled in an investigational drug or device study or has used an investigational drug or investigational device treatment within 30 days prior to Visit 2 (Baseline).
13. Subject has lesions suspicious for skin cancer (skin cancer not ruled out by biopsy) or untreated skin cancers within the Treatment/Assessment Areas.
14. Subject has a physical condition or other dermatologic disorder that, in the Investigator's opinion, might impair evaluation of CI, or that exposes the subject to unacceptable risk by study participation.
15. Subjects with ALT or AST $> 2 \times$ Upper Limit of Normal (ULN) and creatinine $> 1.5 \times$ ULN.
16. Subject is unable to communicate or cooperate with the Investigator due to language problems, impaired cerebral function, or physical limitations.
17. Subject has a history of drug or alcohol abuse within the past 6 months, or if suspected to be noncompliant or is unlikely to comply with the requirements of the study protocol (eg, due to alcoholism, drug dependency, mental incapacity) in the opinion of the Investigator.
18. Subject has a history of sensitivity to any of the ingredients in the study treatments (see [Section 6.1](#)).

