In addition, in a Phase 2a clinical study of subjects with CI, the concentrations of isotretinoin and tretinoin were measured. Plasma concentrations of isotretinoin and tretinoin indicated that systemic exposure was minimal within the 4 hours following initial application. Trough concentrations measured on Days 8, 29, 57 and 84 approximately 12 hours following the preceding dose indicated that systemic concentrations of isotretinoin and tretinoin were within range of the endogenous levels measured at Baseline prior to the first application.

The most notable adverse reactions with oral isotretinoin are: dry lip, dry skin, back pain, dry eye, arthralgia, epistaxis, headache, nasopharyngitis, chapped lips, dermatitis, renal or hepatotoxicity, musculoskeletal discomfort, teratogenicity, and visual acuity reduced.

The following are concerns for women of childbearing potential (WOCBP):

- Severe birth defects can occur during pregnancy while taking oral isotretinoin, with any amount and even if taken for short periods of time;
- Pregnancy must be avoided 1 month before, during, and for 1 month after treatment.

More detailed information about the known and expected benefits and risks and reasonably expected adverse events (AEs) of TMB-001 ointment may be found in the Investigator's Brochure.

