5.4 Screen Failures

Screen failures are defined as subjects who consent to participate in the clinical study but are not subsequently randomized into the study. A minimal set of screen failure information is required to ensure transparent reporting of screen failure subjects to meet the Consolidated Standards of Reporting Trials (CONSORT) publishing requirements and to respond to queries from regulatory authorities. Minimal information includes demography, eligibility criteria, and any serious adverse event (SAE) will be collected and recorded in the electronic data capture system.

Individuals who do not meet the criteria for participation in this study (screen failure) may be rescreened.

Eligible subjects who are not able to complete all their screening assessments within the designated screening period may be rescreened at the discretion of the Sponsor. Rescreening for other reasons may be allowed after consultation with the Sponsor. All screening assessments except for the ICF/Assent, confirmation of CI diagnosis, height, and buccal swab for DNA will be repeated unless determined otherwise by the Sponsor.

Participants who have a clinically nonsignificant out-of-range laboratory result may be rescreened 1 time only at the discretion of the Investigator and after consultation with the Sponsor. For normal ranges, refer to the Laboratory Manual.

Rescreened subjects should not be assigned the same subject number as for the initial screening.

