8.3.5 Clinical Safety Laboratory Assessments

Urine and blood samples will be collected from each subject for safety laboratory analyses at Visit 1 (Screening) and Visit 6 (EOS).

Subjects must be fasting (at least 8 hours) for Visit 1 (Screening) and, if possible, for Visit 6 (EOS); however, if a subject arrives at the clinic for Visit 6 (EOS) without fasting for at least 8 hours, laboratory specimens may be collected as non-fasting, at the discretion of the Investigator, and with the appropriate fasting status documented on the laboratory requisition form.

For subjects that will have the Visit 6 (EOS) conducted remotely, urine and blood samples may be collected by a home health care provider supplied by the Sponsor.

See [Appendix 3](#) for the list of clinical laboratory tests to be performed and to the Schedule of Activities ([Section 1.2](#)) for the timing and frequency.

The Investigator must review the laboratory report, document this review, and record any clinically relevant changes occurring during the study in the AE section of the eCRF. The laboratory reports must be filed with the source documents. Clinically significant abnormal laboratory findings are those that are not associated with the underlying disease unless judged by the Investigator to be out of range to a greater degree than expected for the subject's condition.

All laboratory tests with values considered clinically significantly abnormal during participation in the study or within 30 days after the last dose of study medication should be repeated until the values, stabilize, return to normal or Baseline, or are no longer considered clinically significant by the Investigator or Medical Monitor.

- If such values do not return to normal/Baseline within a period judged reasonable by the Investigator, the etiology should be identified, and the Sponsor should be notified.

- All protocol-required laboratory assessments, as defined in [Appendix 3](#), must be conducted in accordance with the laboratory manual and the Schedule of Activities ([Section 1.2](#)).
- If laboratory values from non-protocol-specified laboratory assessments performed at the institution's local laboratory require a change in subject management or are considered clinically significant by the Investigator (eg, SAE, AE, dose interruption), then the results must be recorded in the eCRF.

Any new or worsening of clinically significant abnormalities at Visit 6 (EOS) will be recorded as AEs.

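### Exclusion 15 joins the liver and creatinine limits with *and*, so read literally it excludes only subjects who have both abnormalities

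*Protocol*

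**What the plan says.** The list in Protocol Section 5.2 opens with the rule "A subject is ineligible to enter the study if he/she meets 1 or more of the following criteria". Item 15 on that list begins "Subjects with ALT or AST", sets 2 x ULN as the transaminase limit, and passes to the kidney limit of 1.5 x ULN with the words "Upper Limit of Normal (ULN) and creatinine".

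No other passage in the protocol or SAP gives a liver or creatinine limit for entry. Appendix 3 lists the laboratory tests and refers back to Section 5.0 for eligibility. The SAP does not restate the criterion.

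Three other provisions bear on a subject with an abnormal screening result:

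- Inclusion 8 (Section 5.1) asks that the subject be, in the Investigator's opinion, "in good general health and free of any disease state or physical condition" that might impair evaluation or pose unacceptable risk.
- Exclusion 14 (Section 5.2) covers a condition that, in the Investigator's opinion, might impair evaluation of the disease, "or that exposes the subject to unacceptable risk by study participation".
- Section 5.4 says that a participant with a "clinically nonsignificant out-of-range laboratory result may be rescreened 1 time only", at the Investigator's discretion and after consulting the Sponsor.

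None of the three states a number.

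**The concern.** The opening rule of Section 5.2 chooses between numbered items. It does not separate the two parts within item 15, so the *and* inside that item decides who is excluded. On the literal reading, a markedly raised ALT with normal creatinine passes, and so does a markedly raised creatinine with normal transaminases.

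For such a subject a stated limit becomes site judgement, and two sites can treat the same value differently. The two readings also lead to different actions after enrollment. Section 7.2 requires study treatment to stop in a subject found not to meet the entry criteria. With an isolated abnormality, one reading requires discontinuation and the other does not. The SAP's planned listing of subjects who did not meet the criteria (Listing 16.2.1.2) would differ too.

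The Visit 1 sample is the only scheduled safety laboratory check before dosing: Section 8.3.5 schedules samples at Visit 1 and Visit 6 only. Visit 1 may fall up to 90 days before Baseline. Dosing is then twice daily for 12 weeks on 10% to 90% of body surface area, in subjects from 9 years of age, and Section 9.6 plans no safety monitoring committee.

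**Working it through.** The plan states no figure to reproduce. The check is a truth table and a comparison of wording.

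**Inputs, all from criterion 15.** Let A = 1 if ALT > 2 x ULN, S = 1 if AST > 2 x ULN, and C = 1 if creatinine > 1.5 x ULN; each is 0 otherwise. There are 2 x 2 x 2 = 8 patterns.

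**Rules compared.**

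- As written: exclude if (A or S) and C.
- With *or*: exclude if A or S or C.

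| ALT | AST | Creatinine | As written | With *or* |
|---|---|---|---|---|
| 0 | 0 | 0 | admit | admit |
| 1 | 0 | 0 | admit | exclude |
| 0 | 1 | 0 | admit | exclude |
| 1 | 1 | 0 | admit | exclude |
| 0 | 0 | 1 | admit | exclude |
| 1 | 0 | 1 | exclude | exclude |
| 0 | 1 | 1 | exclude | exclude |
| 1 | 1 | 1 | exclude | exclude |

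The text excludes 3 patterns and the *or* version excludes 7. The difference is 7 - 3 = 4: ALT only, AST only, ALT plus AST with creatinine not above its limit, and creatinine only.

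**Illustrative values (assumed, not from the documents).** ALT of 5 x ULN with normal creatinine gives (1, 0, 0), which is admitted. Creatinine of 3 x ULN with normal transaminases gives (0, 0, 1), also admitted.

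**Usage elsewhere in Section 5.** Alternative grounds within one exclusion are usually joined by *or*: criterion 1 (pregnancy, lactation or planned pregnancy), criterion 4 (parts a and b) and criterion 8 (retinoids or other systemic therapies) are examples. Where Section 5.1 needs two conditions together, in inclusion 6, it uses a capitalised *AND*. Criterion 15 itself uses *or* between ALT and AST before changing to *and*. A site following this usage would read criterion 15 as needing both abnormalities.

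**The case against.** The strongest reply is that the sentence has a second grammatical reading. Criterion 15 is the only exclusion phrased in the plural, and a list of subjects with X and Y can mean those with X together with those with Y. The context favours that intent. Section 2.3 names kidney and liver toxicity as alternatives among the notable reactions to oral isotretinoin, and Section 5.4 speaks of a single out-of-range result leading to rescreening. The protocol gives no reason for wanting both abnormalities together. This reading is possible and probably what the sponsor meant. It supports correcting the wording: if either abnormality was meant to exclude, the text should say so.

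A second reply is that other safeguards exist. Inclusion 8 and exclusion 14 are mandatory, the Investigator must review each laboratory report, clinically significant abnormal values are to be repeated (Section 8.3.5), and Appendix 3 allows additional tests at any time. These make it less likely that a subject with a marked isolated abnormality is enrolled. They still set no threshold.

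A third reply is that little harm would follow. Section 2.3 reports that in Phase 2a "systemic exposure was minimal within the 4 hours following initial application" and that trough levels stayed within the endogenous range. Section 8.5 says that swallowing a tube of the 0.1% ointment would give less exposure than recommended oral dosing. This stands and limits the weight of the point.

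Finally, the pattern count does not measure how many subjects are affected, and an amendment involves more than changing a word. Both are fair. The waiver provisions do not settle the meaning: Section 5.0 bars waivers of enrollment criteria, while Section 8.0 allows waivers at the Sponsor's discretion, and neither says how criterion 15 should be read.

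**Conclusion.** The concern holds. As written, the only numerical organ-function limit excludes 3 of 8 abnormality patterns, against 7 of 8 if either organ's abnormality were enough. The four patterns let through include every isolated liver or kidney abnormality, which the limit appears meant to catch. How many subjects this would involve cannot be derived from the documents.

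The conclusion rests on the literal reading of *and*, and on there being no other liver or creatinine limit in either document. How the eCRF or site materials apply the criterion cannot be seen. The consequence concerns safety screening and consistency across sites. The efficacy analyses are not affected, and with low reported exposure the likely clinical harm is small. The wording should still be corrected, because the rule as it stands differs from its probable intent.

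**What to change.** Reword criterion 15 to exclude a subject with ALT or AST > 2 x ULN, **or** creatinine > 1.5 x ULN, or list the two limits as separate numbered criteria. Keep both thresholds. Align any eCRF eligibility check with the new wording. If a joint limit was intended, state that and give the reason.

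The text change is one word, but under Appendix 2 an amendment needs IRB/IEC approval and, when applicable, regulatory authority approval. A few more subjects may fail screening, which matters in a rare disease with 45 planned subjects. Section 5.4 already offers one rescreen when the out-of-range result is not clinically significant.
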